8.5. Follow up data collection

8.5.1. Weekly micro-assessments (during the intervention stage)

At week 1, 2, 3, 4, 5, 7, 9, 11, 13, 15, participants will receive prompts to complete brief questionnaires (micro-assessments) via the mPath App. The schedule for these questionnaires will start from the day the participant reinstalls mPath with their second invitation code, provided to them at the point of randomisation. The questionnaires collected during the micro-assessments will include condensed (2-3 item versions) of self-report and brief problem description measures of mediators, as well as brief outcome measures of RNT, anxiety (GAD2), depression (PHQ2), as detailed in Table 3. Participants will also be prompted to complete two brief questions in weeks that the full micro-assessment is not required (weeks 6, 8, 10, 12 and 14). This is to maintain engagement and to keep m-Path live on their phones (i.e., prevent the App from being put to sleep by the operating system).

Participants will have a +4 day window each week to complete the micro-assessments, after which the assessment will no longer be accessible to the participant. If any of the micro-assessments or engagement prompts are not completed, the participant will be sent an email to increase their engagement with the app and reminding them to open the m-Path app to ensure future survey notifications are received (i.e. to avoid the app going into sleep mode).

During the intervention period we will also collect data on engagement with the intervention (see Section 9 for more details).

8.5.2. 16 weeks post-randomisation

At 16-weeks post randomisation, participants will receive an automated SMS text message and an email with a link to complete the follow up questionnaires as surveys via REDCap Academic. On week 16 participants will also be invited to complete EMA for another 10-14 days (see the EMA thresholds under the Baseline Section 8.3) via the m-Path App. The schedule for the EMA will start from the day the participant reinstalls mPath with their second invitation code, provided to them at the point of randomisation. The questionnaires and data collected at 16 weeks post-randomisation are detailed in Table 3.

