As part of our policy for addressing risk and prioritising the welfare of participants, participants are provided with links to online support, the opportunity to request contact from the study team, and automatic signposting to help and guidance if reporting risk (e.g., suicidal thoughts, as indexed in items within the Patient Health Questionnaire-9 (PHQ-9) on the screening or follow-up questionnaires) or significant worsening symptoms suggesting a need for help. These messages include general information on the presenting symptom, recommended actions to make themselves safe, and advice to seek medical help, and direct links to relevant national sources of help. These sources of support will be tailored by participating country. For this purpose, significant worsening symptoms is defined as a deterioration of movement across two or more score categories on the GAD7 or PHQ-9 from baseline to 16-weeks or from baseline to 52-weeks follow-up. At the point of automated signposting, participants can request contact from a study PWP or contact a study PWP via e-mail or telephone to seek advice.

The main indicator of harm will be the completion of the PHQ-9 questionnaire by the participants at baseline and at 16-weeks and 52-weeks post-randomisation. Questionnaires will be automatically screened for signs of severe distress (for example, defined reports of suicidal ideation), with automatic programmed questions following up to ascertain aspects of risk and to automatically provide users

with recommended advice and signpost towards help (GP, local hospital, crisis teams, relevant charities; e.g., website link to the Samaritans). Other indicators would be reports of worsening symptoms or suicidality in direct contact from participants to the research team or in contact with the study PWP (UK)/coach (USA). For participants at 16-weeks, elevated reports of suicidality (as per definition at screening, i.e., endorsing automated follow-up questions 2 or 3) will be followed up by the associated PWP, following an established risk protocol.

PWPs/coaches will maintain a risk log separate from the research database to document interactions with participants who are (or potentially are) 'at risk' and any actions taken to support, guide and/or refer them on to other services. The risk log will not be considered 'research data', but instead will be data pertaining to the clinical care of the participant

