In addition, the number of participants who report significant worsening symptoms of anxiety, or worsening symptoms of depression (as defined above) will be reported to the DMEC, TSC and TMG via regular reports. For all participants, we will include brief open questions at 16-week follow up to assess potential harm from the intervention (e.g., "Have you had any problems with the study treatment? Has any aspect made you feel worse?"), whilst minimizing participant burden. If harm is indicated in these questions, the PWPs will be automatically notified to review the freetext answers and discuss any concerns with the site lead within 3 working days. Number of participants indicating harm in these questions will be reported to the oversight committees via routine reports.

Individuals reporting severe levels of symptoms or meeting diagnostic criteria for depression will be offered guidance to seek appropriate help from their GP or relevant clinical service, should this seem necessary.

For those who are randomised into the study and then indicate risk there will be the option to request contact from a PWP to seek advice. This advice will include guidance for the participant to seek appropriate help from their GP or other relevant services, should this seem necessary. PWPs will be trained in and provided with a protocol to assess risk including standard useful responses in these circumstances. The University of Exeter (UK) study site has a designated site lead/senior clinical psychologist and psychological wellbeing practitioners who will be available as a resource to researchers to provide guidance on clinical issues arising from participants either through standardised measures or contacts initiated by the participant. An equivalent series of expertise is available at UCLA (USA).

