12.1. Definitions

Because the current intervention is digital self-help with PWP(UK)/ coach(USA) support, rather than a medicinal product and involves no biological agent, it is not appropriate to report all adverse events (defined as any untoward medical occurrence). Rather, as a psychological intervention, appropriate adverse events would include those related to mental state and behaviour. We will therefore not report

non-serious adverse events but will report serious adverse events (SAEs) within all intervention groups under our own study-specific definition (see **Table 1**).

As this is a low risk study with no known adverse events associated with the intervention, all related adverse events are unexpected of the intervention.

Table 1: Definitions of adverse events

Term	Definition
AE	Any unintentional, unfavourable clinical sign or symptom, or any new illness or disease or the deterioration of existing disease or illness (not recorded/reported in this study).
SAE	For the purposes of this study, a Serious Adverse Event (SAE) is defined as any of the following events: 
 • Death (including suicide). • Suicide attempt. • New self-harm or an increase in frequency, intensity or duration of self-harm (self-harm is defined as anything with the intention to harm self without the intention to end life including but not limited to; cutting, burning, scratching, hitting). • Serious accident or violent incident requiring emergency medical assistance (including presentation at Accident and Emergency, hospital treatment or ambulance/paramedic callout). • Referral to crisis care or admission to psychiatric hospital. • Admission to A&E for overdose or excessive alcohol or drug use.
Related Unexpected SAE (RUSAЕ)	Any event which meets one or more of the above SAE criteria AND is assessed as being likely to have been caused by the intervention.

All SAEs will be reported to ExeCTU on a SAE form within REDCap. This must be completed within 24 hours of the investigator becoming aware of the event. All SAEs will be onward reported to the Sponsor by ExeCTU. SAEs which are categorised as unrelated to the intervention will be reported monthly by provision of a trial management group (TMG) report.

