13. STATISTICS AND DATA ANALYSIS

13.1. Target sample size and justification

To detect a Minimum Clinically Important Difference of Standardized Mean Difference (SMD) (Cohen's d) = 0.20 (i.e., a small effect size below which any effect is unlikely to be an important mechanism or specific ingredient) with 90% power at $\alpha=0.05$ in main effect of treatment component(s) requires N=1054 (n=527 per level of each factor). Conservatively estimating 52% dropout attrition posttreatment, we require N≈2192 for Analysis of Variance (or equivalent) to test main effects and two-way interactions. Recruitment rates from our prior online trials confirm this target is feasible.

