13.3.3. Secondary outcome analysis

A range of exploratory secondary analyses will be undertaken including but not limited to those specified below with the full analysis being specified in the statistical analysis plan.

8 Weekly Micro Assessments

In addition to the endpoints at 16 and 52 weeks the study also includes multiple weekly micro assessments in order to assess change in hypothesized mechanisms-of-change over time during the course of therapy (recognising that change often happens in first half of therapy), and thereby, test if (a) manipulated treatment components influence hypothesized mechanisms and/or alternative mechanisms (e.g. does presence of Be Kind increase self-compassion more than absence); (b) track any such change over time; (c) enable a test of mediation across multiple time points and with prospective analysis of whether any changes in process measures predicts change in RNT and mediates the effect of factors on change in RNT.

The micro-assessments will be analysed using a repeated measures analysis of variance to assess change in hypothesized mechanisms-of-change over time during the course of therapy as specified prior.

Analysis of PWP/coach effect

The study is supported by a relatively small number of PWPs (UK) and coaches (US). With the initial number employed expected to be fewer than 10. All PWPs and coaches will also be expected to deliver all intervention arms and the PWP/coach will be selected for the participant prior to randomisation. All steps will be taken to minimise the PWP/coach effect and to ensure that it is balanced across treatment conditions. However, as part of our secondary analysis we will still investigate the PWP/coach effect and its potential for impacting on the outcome.

52 Week follow-up analysis

Where possible we will obtain long-term follow-up (52 weeks) on all participants. Analysis will be analogous to the primary analysis using an adjusted multilevel mixed model to investigate the effect of the four treatment factors and their first order interactions.

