14.1. Data collection tools and source document identification

Study data will primarily be collected online. The source data will be the eCRFs held in REDCap Academic, the MyDataHelps platform, and the mPath app. All data will be provided directly by the participant with the following exceptions:

- Data reported by a participant over the telephone that is entered into the eCRF by the research team (e.g. in the case that a participant does not complete the questionnaires and receives a reminder phone call from the research team, and the participant opts to complete the questionnaires over the phone).
- SAE report eCRFs will be completed by the PWP (UK)/coaches (USA)/site leads
- Change of participation status eCRFs will be completed by the research team.
- The participant contact log/appointment log will be completed by the research team/PWP (UK)/coaches (USA).

A full audit trail will be maintained on REDCap Academic, including the date and time data was first recorded, by whom if the user is a staff user (i.e., not a participant) and a full history of amendments made to the original data. Any data that would ordinarily be participant-reported that was entered into the eCRF by a PWP/coach/researcher will be specified so that the source is clearly distinguishable. For the data entered into the m-Path app an audit trail will be automatically logged of the time that each survey or reminder is sent, received, accessed and completed. The entered data cannot be edited by staff or participants on m-Path once it has been submitted.

This is a decentralised trial, with research sites defined at the country level. Each participating country will hold and be in control of their respective data.

PWP/coaches will maintain risk logs separate to the REDCap database, but this will not be included as 'research data'.

Data collected as part of qualitative interviews with participants will be audio-recorded via Teams or Zoom, or using an encrypted GDPR-compliant audio-recording device. Audio-recordings will be the source of the interview-generated data and will be stored until interview analysis is complete. Audio-recordings will be transcribed into Word documents by a third-party transcription service.

USA-specific detail

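### The non-serious harm counts in Section 12 cover only participants who return the 16- or 52-week questionnaires, and the ten in-treatment PHQ-2/GAD-2 readings are not used to supplement them

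*Protocol*

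**What the plan says.** **The harm measure.** Protocol Section 12 says: "The main indicator of harm will be the completion of the PHQ-9 questionnaire by the participants at baseline and at 16-weeks and 52-weeks post-randomisation". Significant worsening is a move of two or more score categories on the GAD-7 or PHQ-9 between baseline and 16 weeks, or between baseline and 52 weeks.

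**What the committees receive.** Section 12 promises the DMEC, TSC and TMG "the number of participants who report significant worsening symptoms of anxiety, or worsening symptoms of depression (as defined above", and also the number who indicate harm in brief open questions at the 16-week follow-up.

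**What is not kept.** The adverse event definition in Section 12.1 includes "the deterioration of existing disease or illness (not recorded/reported in this study"; only serious events are reported. Worsening or suicidality raised with a PWP or coach is a further indicator of harm, but it is documented in a log of which Section 12 says: "The risk log will not be considered 'research data".

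**Expected loss.** Section 13.1 sets the sample size with the words "Conservatively estimating 52% dropout attrition posttreatment".

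**What is collected during treatment.** Section 8.5.1 schedules micro-assessments in weeks 1, 2, 3, 4, 5, 7, 9, 11, 13 and 15, which include "brief outcome measures of RNT, anxiety (GAD2), depression (PHQ2), as detailed in Table 3". Section 13.3.3 gives their analysis: "The micro-assessments will be analysed using a repeated measures analysis of variance to assess change in hypothesized mechanisms-of-change over time during the course of therapy". Sections 12 to 12.4 do not mention the micro-assessments, PHQ-2 or GAD-2.

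**The concern.** A person who deteriorates and does not return a follow-up questionnaire appears in neither count. Section 2 accepts that a small percentage of patients can deteriorate in psychological treatment and promises to assess harms. Section 12 says that users who do not benefit will most likely disengage. It is therefore unsafe to assume that non-returners resemble returners.

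At stake is how many people the oversight committees and the final report can say got worse. The protocol already holds repeated symptom readings taken before the 16-week questionnaire is due, and Section 12 leaves them out.

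**Working it through.** **1. The plan's own sample size.** Inputs from Section 13.1: SMD 0.20, power 90%, alpha 0.05 (taken as two-sided), attrition 52%.
- The t-test calculation gives 526.33 per level, rounded up to 527, so 1,054 in total, as stated. The normal approximation gives 526 per level, 1,052 in total.
- Inflation: 1,052 / (1 − 0.52) = 2,192, as stated; 1,054 / 0.48 = 2,196. The figure reproduces.

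**2. Who falls outside the 16-week counts.**
- 52% attrition: 2,192 × 0.52 = 1,139.8, about 1,140 outside; about 1,052 inside.
- 30% attrition (assumed): 2,192 × 0.30 = 657.6, about 658 outside.

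The 52% is read as net of all follow-up effort. The 1,140 is not a strict upper bound for missing PHQ-9/GAD-7, because the last telephone step in Section 8.5.2 collects the primary outcome only.

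**3. How many worsened people might be missed.** The protocol gives no deterioration rate. Assume 2% to 10%, unrelated to dropout.
- Deteriorated: 2,192 × 0.02 = 43.8 to 2,192 × 0.10 = 219.2.
- Not counted at 16 weeks with 52% attrition: 43.8 × 0.52 = 22.8 to 219.2 × 0.52 = 114.0, about 23 to 114.
- With 30% attrition: 43.8 × 0.30 = 13.1 to 219.2 × 0.30 = 65.8, about 13 to 66.

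Some may be picked up at 52 weeks if they respond then.

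**4. Other routes.**
- Withdrawals and reasons go to the committees, but people lost to follow-up are not classed as withdrawn (Section 11).
- People who drop out of the intervention are invited to give reasons on an online form (Section 10); this is not a symptom score.
- SAEs are reported to 20 weeks, serious events only (Sections 12.1 and 12.3).
- Section 14.1 allows for the case where "the participant opts to complete the questionnaires over the phone"; such people count as returners.
- 52-week worsening and diagnostic incidence exist only for 52-week responders.

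None of these gives a symptom-worsening count during treatment for someone who does not return the 16-week questionnaire.

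**5. The high-versus-low contrast, as illustration only.** All rates here are assumed. Take 1,096 per level, true deterioration 8% v 5% (87.7 v 54.8 people, 142.5 in total, ratio 1.60), and 48% response among everyone who has not deteriorated.

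| Response among the deteriorated, high / low | Observed, high | Observed, low | Ratio | Counted of 142.5 |
|---|---|---|---|---|
| 48% / 48% | 42.1/526.1 = 8.0% | 26.3/526.1 = 5.0% | 1.60 | 68.4 |
| 30% / 30% | 26.3/510.3 = 5.15% | 16.4/516.2 = 3.18% | 1.62 | 42.7 |
| 30% / 48% | 26.3/510.3 = 5.15% | 26.3/526.1 = 5.0% | 1.03 | 52.6 |

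In the first two rows the absolute count falls and the ratio holds. The contrast is lost only in the third row, where dropout among deteriorated people differs by level.

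**The case against.** The strongest reply is that this is an omission, and that the protocol defers to a statistical analysis plan not at hand. Section 13.3.3 says its list of analyses is not complete. The DMEC may request interim analyses (Section 13.4), sees unblinded disaggregated data (Section 15), and could ask for the table. Section 13.6 promises imputation of missing secondary outcomes, which include PHQ-9 and GAD-7, so the final symptom comparisons are not confined to returners. Serious harm is defined broadly and can be detected through staff contact (Sections 12.1 and 12.3).

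Part of this stands. Serious events remain visible, and imputation helps the final comparison of scores. But Section 12 itself chooses the harm measure and specifies what the committees routinely receive. A right to ask is not a planned report, and imputation does not change the running count.

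Two stronger readings are tempting, and the documents do not support them.
- **The committees cannot interpret the counts because no denominator is named.** They do receive the number and proportion of incomplete questionnaires (Section 17.5) and review completeness (Section 15), so an overall denominator can be derived. Printing it beside the count is a reporting detail.
- **The comparison between factor levels is biased.** That needs deterioration-related dropout to differ by level. The remark about disengagement in Section 12 does not show this.

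It is also fair to say that PHQ-2 and GAD-2 cannot replace the main measure: the two-category rule does not apply to them, and they have no suicidality item.

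**Conclusion.** The point holds as a gap in coverage. The absolute number of participants who worsen is understated by an unknown amount, while relevant in-treatment data go unused for safety. The size of the uncovered group rests on the protocol's planning figure of 52%, which is not an observed rate. The 23 to 114 missed cases rest on an assumed deterioration rate that is unrelated to dropout. No claim is made about bias between factor levels or about serious harm. This is a worthwhile, inexpensive improvement; it does not invalidate the safety plan.

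**What to change.** Keep PHQ-9/GAD-7 worsening as the main measure. Add to Section 12 one supplementary table for the DMEC reports and the final report:

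- **Who:** all randomised participants with at least one in-treatment PHQ-2 or GAD-2 reading.
- **What:** the number and proportion whose last in-treatment PHQ-2 or GAD-2 has risen from the same items of the screening PHQ-9 or baseline GAD-7 by a fixed amount. A rise of 2 or more points is one example; the value is an assumption, to be set before unblinded data are seen.
- **Layout:** by high versus low level of each factor and, pooled over factors, by 16-week completion. With the two scales shown separately this is 4 × 2 × 2 = 16 proportions plus 2 × 2 = 4.
- **Alongside:** the week of the last reading and the number with no reading.

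**Cost.** A few lines of text and one table. There is no new data collection, participant burden or change to care. Micro-assessment data already reach the CTU at least 6-monthly (Section 14.2), and aggregate SAE data already go to the DMEC biannually (Section 12.3).

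**Downsides.** Two-item scores are noisy. Early readings in dropouts may reflect temporary distress, which Section 12 expects, and would be set against later readings in completers; hence the week of reading. The screening PHQ-9 can precede randomisation by about six weeks (two weeks to consent plus four for baseline, Sections 8.2 and 8.3). Readings start only once m-Path is reinstalled (Section 8.5.1), so the earliest dropouts may have none. The separate voucher for six or more micro-assessments (Section 8.1.2) gives some reason to expect readings from people who later miss the 16-week questionnaire, but the share is unknown.

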12.1. Definitions

Because the current intervention is digital self-help with PWP(UK)/ coach(USA) support, rather than a medicinal product and involves no biological agent, it is not appropriate to report all adverse events (defined as any untoward medical occurrence). Rather, as a psychological intervention, appropriate adverse events would include those related to mental state and behaviour. We will therefore not report

non-serious adverse events but will report serious adverse events (SAEs) within all intervention groups under our own study-specific definition (see **Table 1**).

As this is a low risk study with no known adverse events associated with the intervention, all related adverse events are unexpected of the intervention.

Table 1: Definitions of adverse events

Term	Definition
AE	Any unintentional, unfavourable clinical sign or symptom, or any new illness or disease or the deterioration of existing disease or illness (not recorded/reported in this study).
SAE	For the purposes of this study, a Serious Adverse Event (SAE) is defined as any of the following events: 
 • Death (including suicide). • Suicide attempt. • New self-harm or an increase in frequency, intensity or duration of self-harm (self-harm is defined as anything with the intention to harm self without the intention to end life including but not limited to; cutting, burning, scratching, hitting). • Serious accident or violent incident requiring emergency medical assistance (including presentation at Accident and Emergency, hospital treatment or ambulance/paramedic callout). • Referral to crisis care or admission to psychiatric hospital. • Admission to A&E for overdose or excessive alcohol or drug use.
Related Unexpected SAE (RUSAЕ)	Any event which meets one or more of the above SAE criteria AND is assessed as being likely to have been caused by the intervention.

All SAEs will be reported to ExeCTU on a SAE form within REDCap. This must be completed within 24 hours of the investigator becoming aware of the event. All SAEs will be onward reported to the Sponsor by ExeCTU. SAEs which are categorised as unrelated to the intervention will be reported monthly by provision of a trial management group (TMG) report.

SAEs which are categorised as related to the intervention (Related Unexpected SAE (RUSAЕ)) will be reported to the Sponsor using a SAE template report form produced by ExeCTU. ExeCTU will report RUSAЕs to the Sponsor as soon as reasonably practicable after becoming aware of the event, taking into account that the Sponsor must report the event to the REC within 15 calendar days.

SAEs may be detected by the research team via interaction with the participant and some will be detected by data submitted by participants on the assessment forms in which case, it may not always be possible to obtain full details of an event before submitting the initial report. The research team (typically PWP) will endeavour to make contact with the participant by email and telephone to obtain as much detail as possible and signpost to relevant support if appropriate. All attempted and actual contacts will be documented on a contact log.

